4. ANALYSIS POPULATIONS

The following analysis populations will be defined for this study.

4.1. SAFETY POPULATION

The primary population of analysis for all analyses will be the Safety population. The Safety population will consist of all subjects who receive at least one dose of study treatment during ARC004.

4.2. COMPLETER POPULATION

The Completer population will include all subjects in the safety population who have at least one evaluable maintenance or exit DBPCFC, where an evaluable DBPCFC is defined as completion of at least the peanut part of the food challenge.

Sponsor: Aimmune Therapeutics, Inc.

Protocol: ARC0004

Version: Version 1.0, 10Jul2019

5. PROTOCOL DEVIATIONS

All protocol deviations will be reported on a specific case report form (CRF) as follows:

- Inclusion Criteria
- Exclusion Criteria
- Received incorrect study treatment
- Randomization issue/ randomized to wrong stratum
- ICF
- SAE Not Reported
- Visit Out of Window
- Missed Study Visit
- Procedure Not Per Protocol
- Prohibited Concomitant Medication
- Lab Sample missed
- Study Drug Compliance
- Other (with free text field to record detail)

Protocol deviations will be reviewed and categorized into major or minor prior to database lock. If the PP population is defined, the major protocol deviations causing exclusion from the PP population will be identified. All major protocol deviations will be listed and included in the study report.

6. GENERAL ASPECTS FOR STATISTICAL ANALYSIS

6.1. STATISTICAL NOTATION AND METHODOLOGY

Unless stated otherwise, the term “descriptive statistics” refers to the number of subjects (n), mean, median, standard deviation, minimum, and maximum for continuous variables and frequencies and percentages for categorical variables.

Unless specified otherwise, the denominator for percentages for categorical data will be based on the number of subjects or observations with non-missing data appropriate for summary purposes. The denominator for percentages for incidence data (such as adverse events) will be based on the number of subjects in the analysis population “at risk”. Select ordinal data may be summarized using both descriptive statistics and counts and percentages of subjects in each category, as appropriate.

Minimum and maximum values will be presented at the precision of the original value, means, medians will be rounded to 1 decimal place greater than the precision of the original value, standard deviations and standard errors will be rounded to 2 decimal places greater than the precision of the original value. Percentages will be rounded to 1 decimal place. Percentages that round down to 0 or up to 100% will be displayed as “<0.1%” and “>99.9%”, respectively. Other statistics (e.g., confidence intervals (CIs)) will be presented using the same general rules outlined above, or assessed for the most appropriate presentation based on the underlying data.

Unless otherwise noted, values reported as greater than or less than some quantifiable limit (e.g., “< 1.0”) will be summarized with the sign suppressed in summary tables and figures, using the numeric value reported. Data will display on subject listings to include the sign.

Summary tables will be presented by group/cohort displayed as Group 1 and Group 2 with Cohort 1, Cohort 2, Cohort 3A, Cohort 3B, and Cohort 3C. For disposition, demographic, and other summaries of baseline and history data, a Total column for both groups combined will be included. For any summaries of events such as adverse events or concomitant medications, event incidences will be summarized in the Safety population separately for the following group/cohort study periods:

- Group 1: IDE and Up-Dosing, all QD Maintenance (including extended maintenance), Overall
- Group 2 Cohort 2: QOD, BIW, and Overall
- Group 2 Cohort 1 (includes QD only)
- Group 2 Cohort 3A (includes QD only)
- Group 2 combined cohorts B and C: QD, QOD, BIW, and Overall
- Group 2 Overall QD

Sponsor: Aimmune Therapeutics, Inc.

Protocol: ARC0004

Version: Version 1.0, 10Jul2019

For subjects in Group 2 who were not able to tolerate BIW or QOD dosing per study design and who subsequently reverted to a QD regimen, safety events for these subjects while on QD will be flagged in listings. Safety data collected after the dosing change will not be summarized in tables but will be presented in separate listings for key safety endpoints.

No summaries for any QW or QOW dosing regimens will be tabulated since no subjects initiated these dosing regimens.

All relevant data collected in the database and any derived data will be included in data listings and unless otherwise noted sorted by age group, group/cohort, subject number, test/measurement, and visit and time point as appropriate.

All statistical methods will be based on the International Conference on Harmonization (ICH)-E9 Guidance for Industry "Statistical Principles for Clinical Trials".

A review of the database will be conducted before database lock. Any decision to amend the planned statistical analysis will be documented in an amendment to the statistical analysis plan and details will be included in the CSR.

If the assumptions underlying the formal statistical methods proposed are not met during the analysis of the final data, an alternative, more appropriate, statistical method will be used and any changes documented in the statistical methods section of the CSR, including the rationale for use.

Additional exploratory analyses of the data will be conducted as deemed appropriate.

These analyses will be fully documented and clearly identified as post-hoc and exploratory.

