Group 2 (former AR101): Subjects who complete the AR101 arm of ARC003 and tolerate a challenge dose of ≥ 443 mg cumulative of peanut protein at the ARC003 Exit DBPCFC are eligible to enroll in ARC004. Group 2 subjects will have undergone the Initial Dose Escalation, Up-dosing, and Maintenance Periods in ARC003 and will therefore enter the ARC004 EM period directly.

Upon entry into the EM phase of the study, Group 2 subjects will be consecutively enrolled into 1 of several cohorts that will conditionally explore an alternate dosing interval regimen over 28-week study periods, illustrated in [Figure 1](#) and as follows:

EM Cohort 1: The first 120 Group 2 subjects to enter ARC004 will comprise Cohort 1, and will continue 300 mg of AR101 QD for 28 weeks before undergoing an Exit DBPCFC (total 28 weeks).

EM Cohort 2: The next 50 Group 2 subjects enrolling in ARC004 will comprise Cohort 2 and will take 300 mg of AR101 QOD for 4 weeks and then BIW (eg, Monday/Thursday) for 24 weeks (total of 28 weeks) as tolerated, before undergoing an Exit DBPCFC.

EM Cohort 3: All remaining subjects recruited into ARC004 will comprise Cohort 3. This cohort will be randomized 1:1:1 to 1 of 3 initial strategies:

- a. 300 mg QD for 56 weeks followed by an Exit DBPCFC (Cohort 3A) (total 56 weeks)
- b. 300 mg QD for 28 weeks, then 300 mg QOD for 4 weeks, then BIW for 24 weeks, as tolerated, followed by an Exit DBPCFC (Cohort 3B) (total 56 weeks)
- c. 300 mg QD for 28 weeks, then 300 mg QOD for 4 weeks, then BIW for 24 weeks, then 300 mg QW for 28 weeks, as tolerated, followed by an Exit DBPCFC (Cohort 3C) (total 84 weeks)

[figure not shown]
In ARC004, Exit DBPCFCs will test to a maximum of 4043 mg cumulative peanut protein to determine the continued efficacy of each alternate dosing schedule. Following the end-of-study visit, each subject's participation in ARC004 ends. The end of the study is defined as the date of the last visit of the last subject.

As per the study design, if subjects were on any other regimen other than QD and were tolerating it well during ARC003, those subjects were allowed to continue on their regimen in ARC004. As per the safety monitoring committee suggestion, all subjects in group 2

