7.7. POOLING

In general for summaries of event data, Group 2 cohorts 3B and 3C will be combined and summarized together. For overall summaries of QD exposure in Group 2, the QD exposure period will be pooled across all Group 2 cohorts.

Sponsor: Aimmune Therapeutics, Inc.

Protocol: ARC0004

Version: Version 1.0, 10Jul2019

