10. SAFETY

Safety will be assessed based on extent of exposure, concomitant medications, physical examinations, and all the safety endpoints defined in [Section 3.2](#).

Unless otherwise noted, safety data will be summarized descriptively and the Safety population will be used for all summaries of safety parameters. Event data such as adverse events will be summarized by study period in 2 parts. Part 1 includes Group 1 study periods of IDE and updosing, maintenance, and overall and Group 2 Cohort 2 periods of QOD, BIW, and overall. Part 2 includes all Group 2 QD AR101 rollovers and summarizes by Cohort 1, Cohort 3A, combined Cohorts 3B and 3C (and their respective periods of QD, QOD, BIW, and Overall), and Overall QD representing all Group 2 QD. In general, safety data will be summarized for age group 4-17 years. Additionally, key safety tables will be presented for 18-55 year old subjects. Safety listings will include all treated subjects, sorted by age group and group/cohort.

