Sponsor: Aimmune Therapeutics, Inc.

Protocol: ARC0004

Version: Version 1.0, 10Jul2019

- Group 2 Cohort 2: QOD, BIW, and Overall
- Group 2 Cohort 1 (includes QD only)
- Group 2 Cohort 3A (includes QD only)
- Group 2 Combined Cohorts 3 B and C: QD, QOD, BIW, and Overall
- Group 2 Overall QD
- Group 1, Group 2 Cohort 1, Group 2 Cohort 2, Group 2 Cohort 3A, Group 2 Cohort 3B, and Group 2 Cohort 3C by Maintenance and Exit DBPCFC

Concomitant non-drug therapies will be listed by subject.

Sponsor: Aimmune Therapeutics, Inc.

Protocol: ARC0004

Version: Version 1.0, 10Jul2019

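### Cheap improvement: the event tables have no Cohort 3A column for EM Weeks 28–56, and no joint one for 3B/3C, so the randomized daily-versus-nondaily contrast is not shown period-matched

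*SAP*

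**What the plan says.** SAP 2.3 says of Cohort 3: "This cohort will be randomized 1:1:1 to 1 of 3 initial strategies". Arm 3A takes QD for 56 weeks. Arms 3B and 3C take QD for 28 weeks, QOD for 4 and BIW for 24; 3C was then to move to weekly dosing until Week 84. The same section records that, on the safety monitoring committee's suggestion, 3C subjects on BIW were to stay on BIW. The notes to its Figure 1 still list 3C at 84 weeks.

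For event summaries, SAP 6.1 lists "Group 2 Cohort 3A (includes QD only") and "Group 2 combined cohorts B and C: QD, QOD, BIW, and Overall". Section 10 repeats the layout as "combined Cohorts 3B and 3C (and their respective periods of QD, QOD, BIW, and Overall"), section 10.2 as "Group 2 Combined Cohorts 3 B and C: QD, QOD, BIW, and Overall", and section 10.14 uses it again for anaphylactic reactions. There is also an Overall QD column, for which SAP 7.7 states that "the QD exposure period will be pooled across all Group 2 cohorts".

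Two further statements in SAP 6.1 matter. For Group 2 subjects who revert from nondaily to daily dosing, "Safety data collected after the dosing change will not be summarized in tables"; these data go to listings. And "No summaries for any QW or QOW dosing regimens will be tabulated since no subjects initiated these dosing regimens".

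SAP 6.4 plans no formal comparisons. Protocol section 9 leaves exploratory comparisons between cohorts to the SAP, and the SAP specifies none for events.

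**The concern.** The study's primary objective concerns alternative dosing intervals, and Cohort 3 holds its only randomized comparison of daily with nondaily dosing. (3B against 3C is also randomized, but both are nondaily after Week 28.) The arms differ only from Week 28, so a clean display would put 3A and 3B+3C side by side over Weeks 28–56. The listed columns do not allow this. A reader has two choices:

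- **3A beside 3B/3C Overall.** This is by randomized arm, but it includes the 28 weeks in which every arm took QD. It also omits events after reversion to QD, an exclusion that can apply only to the nondaily arms.
- **3B/3C BIW beside unsplit 3A or Overall QD.** This isolates nondaily dosing but sets later weeks against a mixture of earlier and later weeks. If 3C stayed on BIW to Week 84, the BIW column also runs past the end of 3A's follow-up.

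Cohort 1 beside Cohort 2 is nearly time-matched, but assignment there followed enrolment order.

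At stake is how clearly the tables can show an increase, or the lack of one, in reactions on nondaily dosing.

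**Working it through.** **The plan's own figure.** The plan states no figure for this layout. Its one safety calculation (SAP 2.4) reproduces: 1 − (1 − 0.004)^400 = 0.799, against the stated 80%. It does not address this contrast.

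**Inputs.** Planned sizes from Protocol 7.8.3: Cohort 1 = 120; Cohort 3 = 175, so n = 175/3 = 58.33 per arm. Durations are from SAP 2.3. No attrition is assumed.

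**Subject-weeks.**
- 3A: 56n = 3,267, of which 28n = 1,633 (50%) fall after Week 28.
- 3B+3C Overall, 3C ending at Week 56: 112n = 6,533, of which 50% are shared QD weeks.
- 3B+3C Overall, all of 3C on BIW to Week 84 (assumption): 140n = 8,167, of which 40% are shared QD weeks and 20% fall after Week 56. Of the BIW time alone, 28/(24 + 52) = 37% falls after Week 56.
- Overall QD: 120×28 + 3n×28 = 8,260 in Weeks 0–28, plus 1,633 later, total 9,893; later share 0.165.

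**Rate model (assumed).** Event rate 1 in Weeks 0–28, r afterwards on QD, and r·t afterwards on nondaily dosing. Then:
- 3A = (1 + r)/2
- Overall = (1 + rt)/2 if 3C ends at Week 56, or (2 + 3rt)/5 if it runs to Week 84
- BIW = rt
- Overall QD = 0.835 + 0.165r

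| True ratio t | r | Overall/3A (3C to 56) | Overall/3A (3C to 84) | BIW/3A | BIW/Overall QD |
|---|---|---|---|---|---|
| 1.0 | 0.8 | 1.00 | 0.978 | 0.889 | 0.827 |
| 1.0 | 1.0 | 1.00 | 1.00 | 1.00 | 1.00 |
| 1.0 | 1.25 | 1.00 | 1.022 | 1.111 | 1.200 |
| 1.5 | 1.0 | 1.25 | 1.30 | 1.50 | 1.50 |
| 2.0 | 1.0 | 1.50 | 1.60 | 2.00 | 2.00 |
| 2.0 | 0.8 | 1.44 | 1.51 | 1.78 | 1.66 |

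Overall against 3A is diluted even without a time trend. BIW against QD columns is distorted only if there is a trend.

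**Subject incidence.** SAP 10.3 gives exposure-adjusted rates for the overall summary and the most frequent terms; 10.13 (epinephrine) and 10.14 (anaphylaxis) specify none. Unequal windows then matter even at a constant rate. With an assumed 28-week incidence of 40% and no regimen effect, 3A over 56 weeks shows 1 − 0.6² = 64.0%, QOD over 4 weeks 1 − 0.6^(4/28) = 7.0%, and BIW over 24 weeks 1 − 0.6^(24/28) = 35.5%. Matched columns would show 40% in both arms.

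**What matched columns would not cure.** Protocol 7.8.2 discontinues nondaily subjects after, among other triggers, two related moderate AEs; the QD rules differ. Suppose that only this trigger acts, there is no regimen effect, and individual rates λ per 28 weeks follow a gamma distribution with shape 0.5 to 1. Expected counted events are 2 − e^(−λ)(2 + λ), and expected time at risk is that quantity divided by λ. Averaging each over λ, the matched rate ratio is 0.96 to 0.98 at a mean of 0.2 events, 0.86 to 0.93 at 0.5, and 0.74 to 0.85 at 1.0. Incidence of a first related AE is not cut short by this trigger, because that event comes before it can act.

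**Precision.** Half-width = 1.96·√[q(1 − q)(1/n₁ + 1/n₂)]. With 58 and 117 subjects: 14.4 points at q = 0.3 and 15.7 at q = 0.5. With 20% lost before Week 28 (46.7 and 93.3): 16.1 and 17.6. The incidences and the loss are assumed.

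**The case against.** The strongest reply is that nothing here is an error. The study is descriptive, the SAP calls the alternative-regimen data exploratory, and the primary endpoint covers the whole study period. The secondary endpoint by treatment period is delivered through regimen periods. Efficacy is already shown separately for 3A, 3B and 3C with exact confidence intervals. SAP 6.1 allows further exploratory analyses, and the table shells are in a separate document. All of this stands. However, analyses added under that allowance must be labelled post hoc, and the protocol had left cohort comparisons to the SAP.

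A reader might infer that nondaily time goes untabulated. The documents do not support that: 3B/3C have QOD and BIW columns. What is missing is the 3A counterpart, a joint nondaily column and the Week 56 cut.

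A reader might also infer that matched columns would recover the true ratio. They need not, because the nondaily-only discontinuation rule removes event-prone subjects from one side. This objection stands, and it decides which measure should lead.

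The size rests on assumed r and t. The only directional statement is in Protocol 1.1: symptoms in earlier oral immunotherapy studies tended to lessen with longer treatment. That favours r below 1 but gives no value for EM. With r = 1 and no regimen effect, every planned rate ratio is already 1.00.

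**Conclusion.** The point holds as an inexpensive improvement to the display. The layout in SAP 6.1, 10, 10.2 and 10.14 shows the only randomized daily-versus-nondaily contrast either diluted by shared QD weeks or mixed with time on treatment and unequal windows. With no time trend, an assumed true rate ratio of 2.0 appears as 1.5 to 1.6, and one of 1.5 as 1.25 to 1.30. With no regimen effect and an assumed later-to-earlier rate of 0.8, BIW would look lower than daily dosing, at 0.889 against 3A or 0.827 against Overall QD.

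It would go too far to conclude that a planned analysis is invalid or that the primary endpoint is biased. The SAP names no comparator for BIW and plans no formal comparison, and the primary endpoint is not defined by these columns. The figures rest on planned sizes, no attrition, the assumed r and t and, for the upper dilution figures, 3C staying on BIW to Week 84. The shells could not be checked.

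**What to change.** In SAP 6.1 and 10, and consistently in 10.2, 10.13 and 10.14:

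1. Add exploratory columns for 3A and for 3B+3C over EM Weeks 28–56, by randomized arm, among subjects still in the study at Week 28. They can be limited to key tables: treatment-related AEs, SAEs, anaphylaxis and epinephrine use.
2. Cut by date. Counting from the first ARC004 dose (SAP 7.5), Weeks 28–56 are study days 197 to 392 (28×7 + 1 to 56×7), the same in both columns. Visits are a poor cut: 3C's Week 56/57 visit is scheduled to start weekly dosing, which no subject did.
3. Lead with subject incidence or time to first event, with a descriptive 95% confidence interval for the difference, and give exposure-adjusted rates alongside.
4. Show a second version that keeps events recorded in ARC004 after reversion to QD under the randomized arm. Note that such follow-up exists only where ARC008 was unavailable and includes Repeat Up-dosing (Protocol 3.1.3, 3.1.5).
5. Keep the planned columns and label Overall QD as descriptive only.
6. State the limits: open-label treatment, loss before Week 28, follow-up ending on transfer to ARC008, and the nondaily-only discontinuation rule in Protocol 7.8.2, which can bias recurrent-event rates low in the nondaily column.

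Cost: a few more columns and a second version in selected tables, from data already collected, with no new visits. The drawback is modest precision, about ±14 to 18 points, and wider in tables limited to ages 4–17.
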